3.11 Compliance (Medication Adherence)

Drug accountability data for study treatment will be collected during the study. Any deviation from protocol-directed administration will be reported.

3.12 Extent of Exposure

Extent of Exposure for a participant is defined as the number of cycles and number of days for which the participant receives the study intervention. Summary statistics will be provided on the extent of exposure for the overall study intervention, and for lenvatinib and pembrolizumab separately, for the APaT population.

[figure not shown]
4 APPENDIX

4.1 Region/Country-specific Requirements

4.1.1 China-specific Requirements

[figure not shown]
This section outlines the statistical analysis strategy and procedures for China subpopulation (including China participants randomized in the global portion and China extension portion). China refers to China mainland in this section.

CCI

After the enrollment for the global portion is completed, participants in China will continue to be enrolled in a 1:1 ratio into the lenvatinib plus pembrolizumab arm and the SOC arm until the sample size for the China subpopulation reaches approximately 100 in total (global and China extension portion combined).

CCI

Key elements of the statistical analysis plan for China subpopulation are summarized below. More details are provided in following sections.

Analysis Populations	Efficacy: ITT China subpopulation (including China participants randomized in the global portion and the China extension portion) Safety: APaT China subpopulation (including China participants randomized in the global portion and the China extension portion who received at least 1 dose of study intervention) PRO: PRO will not be analyzed in the China subpopulation
Efficacy Endpoint(s)	Efficacy endpoints are the same as described in Section 3.4.1
Safety Endpoint (s)	Safety endpoints are the same as described in Section 3.4.2
PRO Endpoint(s)	PRO will not be analyzed in the China subpopulation
Statistical Methods for Efficacy Analyses	No formal hypothesis testing is planned, and no multiplicity adjustment will be applied to the analysis for China subpopulation. Unstratified methods will be used for China subpopulation analyses.
Statistical Methods for Safety Analyses	Safety analyses for China subpopulation are the same as those for the global portion as described in Section 3.6.2 if applicable.

Summaries of Baseline Characteristics and Demographics	They are the same for China subpopulation as those for the global portion as described in Section 3.6.4
Analyses Timing	
CCI
 
At the time of global analyses, China subpopulation data including the extension portion may be provided for supportive purpose to fulfill local regulatory needs.

Hypotheses and Multiplicity	No hypothesis testing is planned for the China subpopulation analyses. No multiplicity adjustment will be applied to the analysis of China subpopulation.
Sample Size Calculations	
After the completion of global portion enrollment, the China extension portion will continue to enroll participants and randomize eligible participants until the sample size for the overall China subpopulation reaches approximately 100.
 
CCI

4.1.1.1 Responsibility for Analyses/In-House Blinding

For all China participants, including participants randomized in the global portion and the China extension portion, patient level treatment randomization information will be blinded for a designated team for China analysis within the Sponsor until the China extension portion database lock is achieved.

4.1.1.2 Analyses Timing

[figure not shown]
CCI

However, to increase operational efficiency of the global and China extension portions, if the criteria for conduct of the analyses in the China subpopulation are met before the IA or FA for the global portion, the analysis for China subpopulation may occur at the same time as the IA or FA for the global portion. If the statistical significance for the global portion has been demonstrated at the IA or FA and it is projected that the criteria for conduct of the analysis in China subpopulation including the China extension portion will be met within ~3 months after the IA or FA for the global portion, then the analysis for China subpopulation including the China extension portion may be based on the same database lock as the IA or FA for the global portion.

At the time of global analyses, China subpopulation data including the extension portion may be provided for supportive purpose to fulfill local regulatory needs.

4.1.1.3 Sample Size Calculations

After the completion of global portion enrollment, the China extension portion will continue to enroll participants and randomize eligible participants until the sample size for the overall randomized China subpopulation reaches approximately 100. Participants from China enrolled in the China extension portion of this study after completion of the global enrollment will not be included in the primary analysis population for the global portion.

4.1.1.4 Subgroup Analyses

Analyses may be considered for the China subgroup (i.e., China participants randomized in the global portion only) based on Sponsor's discretion and/or consultation with health authorities if the global interim/final analysis shows positive results and leads to filing and the China subpopulation enrollment has been completed.

4.2 Technical Details for cLDA Model

The cLDA model assumes a common mean across treatment groups at baseline and a different mean for each treatment at each of the post-baseline time points. In this model, the response vector consists of baseline and the values observed at each post-baseline time point. Time is treated as a categorical variable so that no restriction is imposed on the trajectory of the means over time. The cLDA model is specified as follows:

$$E(Y_{ijt}) = \gamma_0 + \gamma_{jt}I(t > 0) + \beta X_i, j = 1, 2; t = 0, 1, 2, 3, \dots k$$

where Y_{ijt} is the PRO score for participant i , with treatment assignment j at visit t ; γ_0 is the baseline mean for all treatment groups, γ_{jt} is the mean change from baseline for treatment group j at time t ; X_i is the stratification factor (binary) vector for this participant, and β is the coefficient vector for stratification factors. An unstructured covariance matrix will be used to model the correlation among repeated measurements. If the unstructured covariance model fails to converge with the default algorithm, then Fisher scoring algorithm or other appropriate methods can be used to provide initial values of the covariance parameters. In the rare event that none of the above methods yield convergence, a structured covariance such as Toeplitz can be used to model the correlation among repeated measurements. In this case, the asymptotically unbiased sandwich variance estimator will be used. The cLDA model implicitly treats missing data as missing at random (MAR).

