3.6.3.2 PRO Completion and Compliance Summary

Completion and compliance of EORTC QLQ-C30, EORTC QLQ-CR29, and EQ-5D by visit and by treatment will be described. Numbers and percentages of complete and missing data at each visit will be summarized.

Completion rate of treated participants (CR-T) at a specific visit for a given instrument is defined as the number of treated participants who complete at least one item on that PRO instrument over the number of treated participants in the PRO analysis population.

$$\text{CR-T} = \frac{\text{Number of treated participants who complete at least one item}}{\text{Number of treated participants in the PRO analysis population}}$$

The completion rate is expected to decrease at later visits during study period for reasons such as study design (e.g., PROs not required following progression), patient discontinuation, etc. Therefore, the compliance rate (CR-E) will also be presented in addition to completion rate. CR E is defined as the number of treated participants who complete at least one item of the instrument over number of participants who are expected to complete the PRO assessment at that visit, excluding participants missing by design such as death, discontinuation, translation not available.

$$\text{CR-E} = \frac{\text{Number of treated participants who complete at least one item}}{\text{Number of treated participants who are expected to complete}}$$

The completion and compliance status will be summarized as below:

- Completed as scheduled
- Not completed as scheduled
- Off-study: not scheduled to be completed.

The reasons for non-completion as scheduled of these measures are collected using “miss_mode” forms filled by site personnel and will be summarized in a table format. The schedule (study visits and estimated study times) and mapping of study visit to analysis visit for PRO data collection is provided in [Table 5](#).

Table 5 PRO Data Collection Schedule and Mapping of Study Visit to Analysis Visit

Treatment Week	Week 0	Week 2	Week 4	Week 6	Week 8	Week 10	Week 12	Week 16	Week 20	Week 24	Week 28
Day	1	15	29	43	57	71	85	113	141	169	197
Range (relative day to first dose date)	[-5, 8]	[9, 22]	[23, 36]	[37, 50]	[51, 64]	[65, 78]	[79, 99]	[100, 127]	[128, 155]	[156, 183]	[184, 211]
Treatment Week	Week 32	Week 36	Week 40	Week 44	Week 52	Week 60	Week 68	Week 76	Week 84	Week 92	Week 100
Day	225	253	281	309	365	421	477	533	589	645	701

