3.6.3.3 Change from Baseline

The time point for the mean change from baseline analysis is defined as the latest time point at which CR-T $\geq 60\%$ and CR-E $\geq 80\%$, and week 8 was selected based on blinded data review prior to the database lock for any PRO analysis.

To assess the treatment effects on the PRO score change from baseline in the EORTC QLQ-C30 global health status/QoL, physical functioning and appetite loss, EORTC QLQ-CR29 bloating scores, and EQ-5D-5L VAS, a constrained longitudinal data analysis (cLDA) model proposed by Liang and Zeger [8] will be applied, with the PRO score as the response variable, and treatment, time, the treatment by time interaction, and the stratification factors used for randomization (see Section 6.3.2 of protocol) as covariates. The treatment difference in terms of least square mean change from baseline will be estimated from this model together with 95% CI. Model-based least square mean with 95% CI will be provided by treatment group for PRO scores at baseline and post-baseline time point.

The technical details on the cLDA model are in the appendix of this sSAP.

Line plots for the empirical mean change from baseline in EORTC QLQ-C30 global health status/QoL, physical functioning and appetite loss, EORTC QLQ-CR29 bloating scores, and EQ-5D-5L VAS score will be provided across all time points as a supportive analysis.

In addition, the model-based LS mean change from baseline to the specified post-baseline time point together with 95% CI will be plotted in bar charts for EORTC QLQ-C30 global health status/QoL scores, all functioning and symptom scores, and for EORTC QLQ-CR29 all functioning and symptom scores.

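### Does leaving the visit set of the PRO longitudinal model open make the Week 8 comparison unfittable or biased?

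*SAP*

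**What the plan says.** SAP Section 4.2 treats time as categorical, constrains the two arms to a common baseline mean, and indexes visits t = 0, ..., k without giving k a value. On the data it says: "In this model, the response vector consists of baseline and the values observed at each post-baseline time point". The first-choice covariance is unstructured. If it does not converge, better starting values are tried (Fisher scoring or another method). Only after that: "In the rare event that none of the above methods yield convergence, a structured covariance such as Toeplitz can be used", with a sandwich variance.

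Section 3.6.3.3 sets the time point for the change analysis: "The time point for the mean change from baseline analysis is defined as the latest time point at which CR-T" is at least 60% and CR-E at least 80%. It then records the outcome: "week 8 was selected based on blinded data review prior to the database lock for any PRO analysis". Model output is described as "PRO scores at baseline and post-baseline time point", in the singular. The bar charts show model means to the one specified time point. The displays across all visits are line plots of empirical means.

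The only list of visits is Table 5 in Section 3.6.3.2, which is the collection schedule and window map. It has 22 time points, baseline plus 21, to Week 100. The same section expects completion to fall, among other reasons because of "PROs not required following progression".

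**The concern.** Read literally, Section 4.2 puts every scheduled visit into the model. Section 3.9 expects 404 PFS events among 434 participants at the interim analysis, about month 18, and questionnaires largely stop at progression. The late visits would then be almost empty and an unstructured matrix over all of them could not be estimated. Non-convergence would be the normal outcome, not the rare one that Section 4.2 foresees.

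The fallback would then carry the analysis. A Toeplitz matrix assigns one correlation to all adjacent visits, whether 2, 4 or 8 weeks apart. The sandwich estimator corrects standard errors but not means. When dropout depends on observed scores, likelihood-based means rely on a correctly specified covariance. At stake would be a biased Week 8 difference from a covariance chosen after a failed fit in an open-label trial.

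**Working it through.** The SAP states no visit count, parameter count or convergence rate for this model, so there is no figure to reproduce.

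**Parameter counts.** An unstructured covariance over T time points has T(T+1)/2 parameters.
- All of Table 5: T = 22, 22 × 23 / 2 = 253.
- Visits reachable by the interim analysis: 18 months is about Day 548. The windows for Weeks 84, 92 and 100 open on Days 562, 618 and 674, so T = 22 − 3 = 19 and 19 × 20 / 2 = 190.
- Baseline and Weeks 2, 4, 6, 8: T = 5, 5 × 6 / 2 = 15.

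**Numbers at each visit.** Inputs from the SAP: 434 participants, 11 months of accrual, cutoffs at months 18 and 25, 404 PFS events at month 18. Assumptions: exponential time on questionnaire, half-rate accrual in the first 2 months. Solving for 404 of 434 events gives a median of about 2.9 months (2.87).
- Week 8 is 8 / 4.345 = 1.84 months, so the expected number is 434 × 2^(−1.84/2.87) ≈ 278. For medians of 2 to 9 months it runs from 229 to 377.
- At month 18: about 12 at Week 52, 5 at Week 60, 1 at Week 68, 0 from Week 84.
- At month 25: about 24 at Week 52, 8 at Week 68, 2 at Week 84, 0.2 at Week 100.

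The 2.9-month median agrees with the plan's own choice of visit. It implies completion of 0.64 at Week 8 and 0.57 at Week 10, so Week 8 is the last visit above 60%.

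**Estimability.** The condition is roughly that each visit has more participants than earlier visits plus the two arm means, and that every pair of visits is jointly observed. In 300 simulated trials per setting, with 10% intermittent missingness (assumed) and medians from 2 to 9 months, the 22-visit model met it in 0% of runs at both cutoffs. The 5-visit model met it in 100%.

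**Effect of the fallback on the reported quantity.** A two-arm simulation used Table 5 spacing, dropout driven by scores and unequal between arms, and two assumed covariances. With Toeplitz over all visits, the bias in the Week 8 between-arm difference was about 0.01 points. A within-arm shift of roughly 0.5 points appeared only when variance increased over time, and it cancelled between arms.

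**Which gaps inform the lag-one correlation.** Under monotone dropout, the number of adjacent pairs equals the number at the later visit. Expected values at month 25, median 2.87:
- 2-week gaps (Weeks 2 to 12): 388.3 + 347.5 + 310.9 + 278.2 + 248.9 + 222.7 = 1796.5
- 4-week gaps (Weeks 16 to 44): 178.3 + 142.7 + 114.3 + 91.5 + 73.2 + 58.6 + 46.9 + 37.6 = 743.1
- 8-week gaps (Weeks 52 to 100): 24.1 + 15.4 + 8.3 + 4.1 + 1.9 + 0.7 + 0.2 = 54.7

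The total is 2594.3. Two-week pairs make up 1796.5 / 2594.3 = 69% and eight-week pairs 54.7 / 2594.3 = 2%. The pooled lag-one value is therefore dominated by the spacing that applies up to Week 8.

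**The case for a change.** The best case for a change is that both readings lead to the same short edit. Section 4.2 speaks of every post-baseline visit, Table 5 is the only list of visits, and no sentence ends the model at Week 8. A programmer working only from Section 4.2 would include everything, and new starting values cannot supply information that the data lack. The fallback is an example with no order of preference. Section 3.6.3.3 plans model-based charts for all QLQ-C30 and QLQ-CR29 functioning and symptom scores, so scales could end up on different covariances. Visits after Week 8 add little, because each of them failed the plan's completeness rule.

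Most of this is correct as description: k and the order of fallback structures are not written down, and a 22-visit unstructured fit would fail. Three links to harm do not hold. First, Section 4.2 never ties its generic index to Table 5, and Section 3.6.3.3, which governs the analysis, points to Week 8. Second, Toeplitz is only an illustration, so an analyst may choose a structure that respects the spacing. The choice of covariance also does not alter the missing-at-random assumption, which concerns the missingness; the fair worry is bias from a wrong working covariance. Third, that bias is negligible for the between-arm difference. A shift in each arm's own mean is not evidence of a shift in the contrast.

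**Conclusion.** The concern does not call for a change. On the natural reading the model has 5 equally spaced visits, 15 covariance parameters and about 278 participants at Week 8; it can be fitted, and a Toeplitz fallback would suit it. On the literal reading the unstructured fit fails, but the fallback still gives a sound Week 8 comparison. The bias of about 0.01 points is 0.01 / 10 = 0.1% of the 10-point deterioration threshold in Section 3.4.3. A single arm's mean change could move by up to about 0.5 points, 5% of that threshold, which would not alter its interpretation.

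The PRO analyses are outside the OS, PFS and ORR alpha scheme of Section 3.8, so no confirmatory conclusion depends on this model. Analysts can be expected to end the model at Week 8, or to choose a workable structure if they do not.

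The conclusion rests on exponential attrition, 10% intermittent missingness in the estimability check, and the covariance and dropout patterns assumed in the two-arm simulation. Estimability was the same across every median tried. The cancellation between arms was seen only under the simulated patterns and is not a general result.

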4.3 Technical Details for Minimal Spending Approach

Below are the technical details for the minimum spending approach.

The Lan-DeMets spending function to approximate an O'Brien-Fleming bound is defined as

$$f(t; \alpha) = 2 - 2\Phi\left(\frac{\Phi^{-1}\left(1 - \frac{\alpha}{2}\right)}{\sqrt{t}}\right)$$

where t in $f(t; \alpha)$ is the spending time, which is not necessarily information fraction or actual time.

The test statistics Z_i at each analysis i is assumed to follow a multivariate normal distribution with expectations $E(Z_i) = \theta\sqrt{I_i}$ and covariances $Cov(Z_i, Z_j) = \sqrt{I_i/I_j}$ where θ is the treatment effect difference of interest and I_i is the actual statistical information available based on the actual observed event number.

To illustrate how the minimum spending approach is implemented, examples with one hypothetical scenario where events accrue faster than expected are given below for the OS analyses with the total alpha of 2.5% (initially allocated). There are 2 planned analyses for OS at IA and FA, respectively.

IA boundary calculation:

For the OS interim analysis at IA, the p-value boundary is the same as alpha spending α_1 determined from the Lan-DeMets spending function. At the time of the analysis, 260 events are expected over the target 336 events at the FA.

- Hypothetical scenario (events accrue faster than expected): 270 events are observed. The spending time is calculated as $t = 260/336 = 77\%$, p-value boundary = 0.0108.

FA boundary calculation:

The alpha spending at the FA is $\alpha - \alpha_1$. FA boundary (C_2) is solved from $P(Z_2 \geq C_2, Z_1 < C_1 | H_0) = \alpha - \alpha_1$, with test statistics Z_1 and Z_2 being multivariate normal and correlations based on observed event numbers.

CCI

CCI

